14.0 Body Fluid Biospecimens

14.1 Summary Table of Research Blood/Blood Products to Be Collected for This Protocol

Indicate if specimen is mandatory or optional	Collection tube description and/or additive (color of tube top)	Volume to collect per tube (number of tubes to be collected)	Blood product being processed and submitted by participating site	Cycles 1-8 Day 1 Pre-treatment	6-8 weeks after Day 1 of Cycle 8	End of Treatment, If discontinued early (At PMD or PD, withdrawal or removal)	At time of PMD or PD	Additional processing required at site after blood draw?	Storage /shipping conditions¹
Mandatory	SST (Marble top)	8.5 ml (1)	Whole blood	X	X	X	X	No	Refrigerated / Do not Freeze
Mandatory	EDTA (purple top)	10 mL (2)	Whole blood	X	X	X	X	No	Refrigerated / Do not Freeze

After all samples have been processed according to kit instructions, ship all specimens according to shipping instructions (see below for detailed shipping instructions.)

14.2 **Kits will be used for this study** and will be contain supplies for collecting, processing and shipping specimens.

14.21 Participating institutions may obtain kits by e-mailing [REDACTED] [REDACTED] E-mail requests should include the site address, contact information and number of kits being requested.

14.22 Kits will be sent via FedEx® Ground at no additional cost to the participating institutions. Please allow 3 to 4 business days to receive the kits.

14.23 Any questions concerning sample collection and [REDACTED] [REDACTED]

14.24 Peripheral Blood
Draw 8.5 mL of peripheral blood into one SST (marbled) collection tube and 20 mL of peripheral blood into two lavender top EDTA tubes. It is important to thoroughly mix the samples with the anticoagulant agent by gently inverting the tubes not less than five times.

14.3 Shipping and Handling

14.31 **Samples are to be collected Monday through Thursday ONLY.** Samples are to be shipped the same day they are collected. **NOTE:** Friday and Pre-Holiday shipments should be avoided.

Samples are to be shipped to:

[REDACTED]
[REDACTED]
[REDACTED]
[REDACTED]
[REDACTED]
[REDACTED]

Please e-mail [REDACTED] to notify the laboratory when specimens are being shipped. The message should include the study name, sample type(s), FedEx airbill tracking number, contact name and telephone number.

14.4 Study Methodology and Storage Information

14.41 Blood/blood product samples will be collected for the following research

14.411 DNA extraction and storage of DNA for future pharmacogenetic assays (e.g., for genetic polymorphisms such as PD-L1/2, EZH2, MEF2B, ARID1A, CARD11, FOXO1, CREBBP and EP300 that may correlate with efficacy and tolerability. [name] laboratory [name] will initially analyze a portion of the DNA for the presence of using standard laboratory protocols. Remaining DNA will be stored frozen at -70°C by [name] Lab, according to patient consent information) until specific analyses are identified. As protocols are developed, they will be presented for ACCRU and IRB review and approval. (This collection is part of a general strategy of investigation for the majority of ACCRU studies.)

- 14.412 A portion of the serum/plasma will initially be analyzed for the presence of Cytokines and T-Cells in [name] laboratory using standard laboratory protocols. According to patient consent information remaining serum/plasma will be stored frozen at -70°C by [name] Lab, until specific analyses are identified. As protocols are developed, they will be presented for ACCRU and IRB review and approval. (This collection is part of a general strategy of investigation for the majority of ACCRU studies.)
- 14.414 As part of ongoing ACCRU research, we will collect serum/plasma for future research studies, according to patient consent information on molecular determinants of efficacy and tolerability. Samples will be stored frozen at -70°C by [name] Lab until specific analyses are identified. As protocols are developed, they will be presented for ACCRU and IRB review and approval.

14.5 Return of Genetic Testing Research Results

For this study, DNA specimens are only being banked and no specific genetic testing is being performed. If, at any time, genetic results are obtained that may have clinical relevance, IRB review and approval will be sought regarding the most appropriate manner of disclosure and whether or not validation in a CLIA-certified setting will be required. Sharing of research data with individual patients should only occur when data have been validated by multiple studies and testing has been done in CLIA-approved laboratories.

14.51 Peripheral blood assays

- 14.511 Serum cytokine analysis: Serum cytokine levels have been shown to be prognostic in Hodgkin lymphoma [Marri]. Samples will be subjected to multiplex ELISA (Invitrogen, Camarillo, CA) to measure 30 serum cytokines in pre-treatment blood samples. Luminex-200 system version 1.7 will be used for reading plates and MasterPlex QT1.0 system (MiraiBio) will be used to analyze data. Cytokines will include epidermal growth factor (EGF), eotaxin, basic fibroblast growth factor (FGF-b), granulocyte macrophage colony stimulating factor (GM-CSF), hepatocyte growth factor (HGF), IFN- α , IFN- γ , interleukin 1 receptor antagonist (IL-1RA), IL-1 β , IL-2, IL-2R, IL-4, 5, 6, 7, 8, 10, 12, 13, 15, 17, Inducible protein-10 (IP10/CXCL10), monocyte chemotactic protein 1 (MCP-1), monokine induced by interferon γ , (MIG/CXCL9), MIP-1 α (CCL3), MIP1 β (CCL4), regulated on activation normal T-cell expressed and secreted (RANTES), TNF- α and vascular endothelial growth factor (VEGF). Internal control serum will be included in all assays to control for interassay variation.
- 14.512 Flow cytometry: To define changes in peripheral blood cell populations after treatment with brentuximab vedotin and nivolumab, peripheral blood mononuclear cells will be stained with fluorochrome-conjugated antibodies to human CD69 (R&D Systems), CD3 (clone HIT3a), CD19 (clone 4G7), PD1 (clone EH12.1), CD14 (clone M5E2), CD163 (clone GH1/61), CD21 (clone B-ly4), CD273 (clone M1H18), CD274 (clone M1H1), TIM3 (clone 344823), and CD23 (clone EBVCS-5; all obtained from BD Biosciences) and the data will be analyzed using CellQuest software (Becton Dickinson).

15.0 Drug Information

IND number 128842 (for combination of both drugs)

- Investigator brochures will be available on the ACCRU website.

15.1 Brentuximab vedotin (SGN-35, Adcetris®)

15.11 **Background:** Brentuximab vedotin (SGN-35) is a CD30-directed antibody-drug conjugate (ADC) consisting of three components: 1) the chimeric IgG1 antibody cAC10, specific for human CD30, 2) the microtubule-disrupting agent monomethyl auristatin E (MMAE), and 3) a protease-cleavable linker that covalently attaches MMAE to cAC10. The anticancer activity of brentuximab vedotin is due the binding of the ADC to CD30- expressing cells, followed by internalization of the ADC-CD30 complex, and the release of MMAE via proteolytic cleavage. Binding of MMAE to tubulin disrupts the microtubule network within the cell, subsequently inducing cell cycle arrest and apoptotic death of the cell.

15.12 **Formulation:** Brentuximab vedotin is a sterile, preservative-free, white to off-white lyophilized cake or powder, supplied in single-use vials. Each vial of brentuximab vedotin contains brentuximab vedotin, trehalose, sodium citrate, and polysorbate 80.

Brentuximab vedotin is an ADC composed of a CD30 targeted chimeric monoclonal antibody (cAC10) covalently linked, via an enzyme-cleavable linker, to the anti-tubulin agent MMAE. cAC10 has a typical structure of the human IgG1 subclass. Brentuximab vedotin is produced by the chemical conjugation of MMAE to cAC10. Each antibody molecule has, on average, two of its interchain disulfides reduced and the resulting cysteine residues alkylated with SGD-1006 Intermediate (enzyme-cleavable linker + MMAE), leading to a molar ratio of four drugs per antibody.

15.13 Preparation and storage:

Vials containing brentuximab vedotin must be stored under refrigeration at 2-8°C.

If an excursion occurs, refer to the study-specific Stability Data document which has stability data for each product supplied by Seattle Genetics that used in the study. If the excursion is between the Acceptable Low Temperature and the Acceptable High Temperatures (the green range) and does not exceed the Maximum out of Range Time, the excursion does not need to be reported. If the excursion is outside of either the acceptable temperature range (the red range) or time range, the product should be quarantined and the excursion should be reported to Seattle Genetics.

Report excursions using FM-244 Investigational Product Quality Complaints and Temperature Excursions Form. Found as a free standing document on the ACCRU Website.

Reconstitution

1. Reconstitute lyophilized brentuximab vedotin by adding 10.5 mL Sterile Water for Injection, USP to the 50 mg vial, directing the stream to the side of the vial. The concentration of reconstituted brentuximab vedotin is 5 mg/mL with a total volume of 11 mL.
2. Gently swirl the vial until contents are completely dissolved. The vial must not be shaken. Slight “bubbling” of the solution upon reconstitution may be observed.
3. Allow the reconstituted vial to settle for a minute to allow bubbles to dissipate. The reconstituted product should be a colorless, clear to slightly opalescent solution with no visible particulates.

4. Reconstituted vials must be stored under refrigeration (2-8°C) and must be administered within 24 hours of vial reconstitution. Protect infusion bag from direct sunlight until time of use.

Dose Calculation

Actual weight will be used except for patients weighing greater than 100 kg; the dose for patients with weight greater than 100 kg will be calculated based on 100 kg. Brentuximab vedotin dose should be rounded to the nearest whole number of milligrams.

Dose Preparation

1. Transfer the required volume of reconstituted product to an infusion bag. The following bag types are compatible with brentuximab vedotin: polyvinylchloride (PVC), ethylene vinyl acetate (EVA), polyolefin, or polyethylene. Closed System Transfer Devices (CSTDs) can be used in the preparation of brentuximab vedotin.
 2. Dilute reconstituted product in either 0.9% Sodium Chloride Injection, USP, Lactated Ringer's solution, USP, or dextrose 5% in water (D5W), USP. The final concentration of brentuximab vedotin in infusion bag should be in the range of 0.4–1.8 mg/mL.
 3. Gently invert the infusion bag. DO NOT SHAKE.
 4. Prior to administration, inspect the prepared dosing solution (in infusion bag) for any particulate matter or discoloration.
 5. Do not prepare a single dose of brentuximab vedotin using vials from different lots. Use vials from the same lot number for a given dose.
 6. The prepared dosing solution must be stored in an infusion bag under refrigeration (2-8°C) and must be used within 24 hours of vial reconstitution. Protect infusion bag from direct sunlight until time of use.
- 15.14 **Administration:** BRENTUXIMAB VEDOTIN MUST NOT BE ADMINISTERED AS AN IV PUSH OR BOLUS. Brentuximab vedotin should be administered over approximately 30 minutes and cannot be mixed with other medications. In-line filters should not be used during the IV administration.
- 15.15 **Pharmacokinetic information:**
- a) Blood levels – The maximum concentrations for serum PK of brentuximab vedotin ADC following an IV dose of 1.8 mg/kg were typically observed at the end of infusion. The half-life is 4 to 6 days. Minimal to no accumulation was observed with multiple doses with the q3wk regimen. The PK brentuximab vedotin when dosed by body-weight (mg/kg) is associated with body-size. The exposure (AUC) of ADC increases with increasing body size, although the magnitude of this increases is small in relation to the overall variability in ADC exposure. Additionally, this population PK meta-analysis indicated that gender, age, and race do not have a meaningful effect on the PK of brentuximab vedotin and that no dosing adjustment based on these intrinsic factors is recommended in adult patients
 - b) Distribution – Following an IV dose of brentuximab vedotin (1.2 to 2.7 mg/kg), the steady-state volume of distribution was approximately 6 – 10 L, indicating that brentuximab vedotin was primarily limited to the vascular space.
 - c) Metabolism and Excretion – The primary route of excretion of MMAE was via feces, whereas urinary excretion was moderate. Intact MMAE was the primary

species excreted and MMAE was excreted in both feces (72%) and urine (27%), suggesting a low propensity for metabolism-based biotransformations. The terminal half-life ($t_{1/2}$) is approximately 4 to 6 days.

Hepatic/Renal Impairment: Patients with hepatic impairment (Child-Pugh class A to C) and patients with severe renal impairment ($\text{CrCl} < 30 \text{ mL/min}$) exhibited a trend toward moderate decreases in ADC exposure and increases in MMAE exposure. Unless otherwise specified in the clinical study protocol, the recommended starting dose in patients with hepatic impairment or severe renal impairment is 1.2 mg/kg administered as an intravenous infusion over 30 minutes every 3 weeks. Clinical studies evaluating the effect of renal or hepatic impairment on the PK of brentuximab vedotin have not yet been done in patients with diseases other than cancer; therefore, it is unknown if these findings are applicable to treating non-cancer patients (e.g., patients with autoimmune liver disease or lupus nephritis) with brentuximab vedotin who have hepatic or renal impairment.

- 15.16 **Potential Drug Interactions:** In vitro data indicate that monomethyl auristatin E (MMAE) is a substrate and an inhibitor of CYP3A4/5. Co-administration of brentuximab vedotin with ketoconazole, a potent CYP3A4 inhibitor, increased exposure to MMAE by approximately 34%. Patients who are receiving strong CYP3A4 inhibitors concomitantly with brentuximab vedotin should be closely monitored for adverse reactions. Co-administration of brentuximab vedotin with rifampin, a potent CYP3A4 inducer, reduced exposure to MMAE by approximately 46%.

Brentuximab vedotin is not expected to alter the exposure to drugs that are metabolized by CYP3A4 enzymes.

Concomitant use of brentuximab vedotin and bleomycin is contraindicated due to pulmonary toxicity that occurred in some patients receiving this combination of treatments.

- 15.17 **Known potential toxicities:**

Very common known potential toxicities, $\geq 10\%$:

Cardiovascular: Peripheral edema

Central nervous system: Neuropathy, peripheral sensory neuropathy, fatigue, peripheral motor neuropathy, headache

Dermatologic: Pruritus, alopecia, maculopapular rash

Endocrine & metabolic: Weight loss

Gastrointestinal: Nausea, diarrhea, vomiting, decreased appetite, abdominal pain, constipation

Hematologic & oncologic: Neutropenia, anemia, thrombocytopenia

Immunologic: Antibody development

Neuromuscular & skeletal: Arthralgia, myalgia, asthenia, muscle spasm

Respiratory: Upper respiratory tract infection, cough, dyspnea

Miscellaneous: Fever

Common known potential toxicities, 1% - $<10\%$:

Central nervous system: Chills

Dermatologic: Cellulitis

Hepatic: Hepatotoxicity

Respiratory: Pulmonary toxicity, pneumonia

Uncommon and rare known potential toxicities, $<1\%$, post marketing and/or case reports: Acute pancreatitis, acute respiratory distress syndrome, anaphylaxis, bacteremia, enterocolitis, febrile neutropenia, gastrointestinal erosion, gastrointestinal hemorrhage,

gastrointestinal perforation, gastrointestinal ulcer, hyperglycemia, increased serum bilirubin, increased serum transaminases, interstitial pulmonary disease, intestinal obstruction, JC virus infection, neutropenic enterocolitis, opportunistic infection, pancreatitis, pneumonitis, progressive multifocal leukoencephalopathy, sepsis, septic shock, serious infection, severe hepatotoxicity, Stevens-Johnson syndrome, toxic epidermal necrolysis

Hyperglycemia has been reported with BV, notably in patients with high Body Mass Index or preexisting hyperglycemia. Any patient, with or without diabetes, who experiences an event of hyperglycemia should have their serum glucose closely monitored. Antidiabetic treatment should be administered, as appropriate.

See the current version of the Investigator's Brochure for more comprehensive toxicity data.

15.18 Drug procurement:

15.181 Brentuximab vedotin will be provided in 50mg vials free of charge from Seattle Genetics for investigational use to Almac, Inc. Each participating ACCRU treating location will order the drug from Seattle Genetics/Almac, Inc. E-mail or Fax the Drug Order Request Form (found on the ACCRU website) to:

Note: Allow 7 business days to process drug order requests.

[REDACTED]
[REDACTED]
[REDACTED]

Each participating ACCRU treating location will be responsible for monitoring the supply of Brentuximab Vedotin and Nivolumab and will use the appropriate Drug Order Request Form to order additional supplies as needed.

Outdated or remaining drug is to be destroyed on-site as per procedures in place at each institution.

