3.0 Patient Eligibility

Prior to discussing protocol entry with the patient, call the [REDACTED] for dose level and to ensure that a place on the protocol is open to the patient.

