3.1 Registration – Inclusion Criteria

3.11 Classical Hodgkin Lymphoma determined by local hematopathology review

3.12 One of the following:

- Age \geq 60 years
- Age <60 years but unsuitable for standard chemotherapy because of a cardiac ejection fraction of <50%, a pulmonary diffusion capacity <80%, or a creatinine clearance \geq 30 and <60 mL/min, or refused standard chemotherapy despite efforts to convince them otherwise.

Cockcroft-Gault Equation:

$$\text{Creatinine clearance for males} = \frac{(140 - \text{age})(\text{weight in kg})}{(72)(\text{serum creatinine in mg/dL})}$$

$$\text{Creatinine clearance for females} = \frac{(140 - \text{age})(\text{weight in kg})(0.85)}{(72)(\text{serum creatinine in mg/dL})}$$

- 3.13 Requirement for systemic chemotherapy: all stages except IA (not bulky disease), if involved field is considered Radiotherapy (RT) curative.
- 3.14 Previously untreated with either chemotherapy, radiation therapy or either brentuximab vedotin or nivolumab, or another check point inhibitor.
- 3.15 ECOG Performance Status (PS) 0, 1, or 2 (Appendix II)
- 3.16 The following laboratory values obtained ≤ 7 days prior to registration.
- Absolute neutrophil count (ANC) $\geq 1500/\text{mm}^3$, unless secondary to bone marrow involvement.
 - Leukocytes $\geq 3,000/\text{mm}^3$
 - Platelet count $\geq 100,000/\text{mm}^3$
 - Hemoglobin >9.0 g/dL – unless determined by treating physician to be disease related
 - Total bilirubin ≤ 1.5 x upper limit of normal (ULN)
 - Aspartate transaminase (AST) ≤ 2.5 x ULN
 - Alanine Transaminase (ALT) ≤ 2.5 x ULN
 - Creatinine ≤ 2.0 mg/dL
 - Amylase and/or lipase ≤ 1.5 x ULN
- 3.17 Women of childbearing potential must have a negative serum or urine pregnancy test (minimum sensitivity 25 IU/L or equivalent units of HCG) within 24 hours prior to registration

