7.22 Treatment Schedule

Agent	Dose Level	Route	Day	Cycle Length
Brentuximab vedotin	1.8 mg/kg (cap at 180 mg) in 100 to 250 mL NS to final concentration 0.4 mg/mL to 1.8 mg/mL	IV infused over 30 minutes, before nivolumab	Day 1	Cycles 1-7 (21 days) Cycle 8 (6-8 weeks)
Nivolumab	3 mg/kg in 100 cc NS	IV infused over 60 minutes. 1 hour after completion of Brentuximab vedotin	Day 1	

7.222 The dosing calculations should be based on the actual body weight at baseline. If the subject's weight on the day of dosing differs by > 10% from the weight used to calculate the original dose, the dose must be recalculated. All doses should be rounded to the nearest milligram. Subjects should be carefully monitored for infusion reactions during nivolumab administration. If an acute infusion reaction is noted, subjects should be managed according to Protocol Section 9. Doses of nivolumab may be interrupted, delayed, or discontinued depending on how well the subject tolerates the treatment. Nivolumab Injection, 100 mg/10 mL (10 mg/mL) and 40 mg/mL (10 mg/mL) Nivolumab injection is to be administered as an IV infusion through a 0.2-micron to 1.2-micron pore size, low-protein binding polyethersulfone membrane in-line filter at the protocol-specified doses. It is not to be administered as an IV push or bolus injection. Nivolumab injection can be infused undiluted (10 mg/mL) or diluted with 0.9% Sodium Chloride Injection, USP or 5% Dextrose Injection, USP to protein concentrations as low as 1 mg/mL. Care must be taken to assure sterility of the prepared solution as the product does not contain any antimicrobial preservative or bacteriostatic agent.

7.3 For this protocol, the patient must return to the consenting ACCRU institution for evaluation at least every 21 days during treatment (with the exception of Cycle 8). After therapy completion, the patient must return to the institution, every 30 days x 90 days, then every 60 days x 180 days, then every 90 days x 2 years, then every 6 months until 5 years post registration, during observation (Active Monitoring Phase) until the patient goes to event monitoring per Section 13.0.

7.4 Patients will be treated for a planned maximum of 8 cycles.

7.5 A PET-CT scan will be performed within 5 days prior to starting cycle 3. Patients who

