8.1 Dose Levels (Based on Adverse Events in Tables 8.2)

Brentuximab Vedotin	
	Starting Dose 1.8 mg/kg IV Day 1
1 st dose reduction	1.2 mg/kg IV Day 1
2 nd dose reduction	Discontinue

Nivolumab	
	Starting Dose 3.0 mg/kg IV Day 1
1 st dose reduction	Discontinue

Note: If either drug is discontinued, the patient may continue treatment with the other drug. If both drugs are discontinued, the patient will go to event monitoring per Section 18.0.

8.2 **Recommended Brentuximab Vedotin (BV) and Nivolumab Dose Modifications for Treatment-Associated Toxicity**

→ → Use the NCI Common Terminology Criteria for Adverse Events (CTCAE) version 4.0* unless otherwise specified ← ←			
CTCAE System/Organ/Class (SOC)	ADVERSE EVENT	AGENT	ACTION**
AT TIME OF RETREATMENT			
Investigations	Platelet count decreased	Brentuximab Vedotin (BV) and Nivolumab	Grade 3: Hold both BV and nivolumab until grade 2 or better, then reinstitute BV at 1.2 mg/kg and resume nivolumab at same dose.

→ → Use the NCI Common Terminology Criteria for Adverse Events (CTCAE) version 4.0* unless otherwise specified ← ←			
CTCAE System/Organ/Class (SOC)	ADVERSE EVENT	AGENT	ACTION**
Investigations	
Alanine aminotransferase Increased, Aspartate aminotransferase Increased, and/or Blood bilirubin increased
 
NOTE: increased bilirubin does not factor into dose modifications if secondary to Gilbert's syndrome.
	Brentuximab Vedotin (BV) and Nivolumab	
Grade 2 (>3 to 5 x ULN) AST or ALT elevations: Omit dosing for nivolumab; continue BV at the same dose level. Nivolumab may be resumed if the value improves to Grade 1 (≤ 3 x ULN) or better.
 
Grade 2 Bilirubin elevations (>1.5 to 3 x ULN): Omit dosing for nivolumab; continue BV at the same dose level. Nivolumab may be resumed if the bilirubin improves to Grade 1 (>ULN to 1.5 x ULN) or better.
 
Grade 2 (>3 to 5 x ULN) AST or ALT elevations WITH Grade 2 Bilirubin elevations (>1.5 to 3 x ULN): Hold both nivolumab and BV until ALT/AST value improves to Grade 1 (≤ 3 x ULN) or better and bilirubin value improves to Grade 1 (>ULN to 1.5 x ULN) or better.
 
Grade 3 (AST or ALT, OR Bilirubin elevations): Discontinue nivolumab; hold dosing for BV until toxicity is \leq Grade 2 or has returned to baseline, then resume at the same dose level.
 
Grade 4 (AST or ALT, OR Bilirubin elevations): Discontinue both nivolumab and BV. Patient should go to event monitoring, per Section 18.

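### Creatinine clearance below 30 mL/min is permitted at entry by every route except the under-60 renal route, and the brentuximab vedotin starting dose for these patients is left unresolved

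*Combined protocol and SAP*

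**What the plan says.** **Recommended dose.** Section 15.15 reports a trend in severe renal impairment (clearance below 30 mL/min) toward moderately lower exposure to the antibody-drug conjugate (ADC) and higher exposure to MMAE. It then says: "Unless otherwise specified in the clinical study protocol, the recommended starting dose in patients with hepatic impairment or severe renal impairment is 1.2 mg/kg".

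**Entry.** Section 3.12 admits patients aged 60 or over with no clearance condition. A younger patient may enter if "unsuitable for standard chemotherapy because of a cardiac ejection fraction of <50%, a pulmonary diffusion capacity <80%, or a creatinine clearance" of at least "30 and <60 mL/min, or refused standard chemotherapy despite efforts to convince them otherwise". These are alternatives, so the floor of 30 binds only those who enter for renal reasons. The one renal limit for every patient is in 3.16: "Creatinine ≤ 2.0 mg/dL". The exclusion criteria name no renal threshold; 3.22 and 3.27 rely on judgement about comorbidity and intercurrent illness.

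**Dose given.** Section 7.22 sets BV at "1.8 mg/kg (cap at 180 mg) in 100 to 250 mL NS", and 8.1 gives "Starting Dose 1.8 mg/kg IV Day 1". Dose level 1 in 7.11 is the same. None of the three mentions renal function. A dose of 1.2 mg/kg appears there only as a reduction for adverse events (8.1) or as level -2 for a whole cohort (7.11).

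**The concern.** The clearance floor in 3.12 sits exactly at the threshold in 15.15, but it covers one entry route out of several. A patient under 60 with a clearance of 25 mL/min cannot enter by the renal route. A patient of 85 with the same clearance can enter if creatinine is within the limit, and nothing in the documents explains the difference. A site with such a patient finds 1.8 mg/kg in the dosing sections and 1.2 mg/kg in the drug information, with no statement of which governs.

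At stake is the first dose of an agent whose cytotoxic component tends to reach higher exposure in these patients. There is also a possible effect on the safety phase. Under 7.11 and 16.4, two or more dose-limiting toxicities among the first six patients lead to level -1, which drops nivolumab and keeps BV at 1.8 mg/kg. A toxicity caused by BV exposure in a renally impaired patient could count toward abandoning the combination.

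**Working it through.** The plan gives no figure to reproduce. The question is whether the creatinine limit of 2.0 mg/dL already keeps clearance at or above 30 mL/min.

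**Inputs.** The Cockcroft-Gault equation from 3.12, the limit of 2.0 mg/dL from 3.16, and the threshold of 30 mL/min from 3.12 and 15.15. Ages and weights are assumptions, since the documents give no distribution for either.

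**Equation.** Clearance = (140 − age) × kg × (0.85 if female) / (72 × creatinine).

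**Step 1: clearance at creatinine 2.0 mg/dL** (denominator 72 × 2.0 = 144).

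| Patient | Calculation | mL/min |
|---|---|---|
| Woman 70, 60 kg | 3570 / 144 | 24.8 |
| Woman 80, 60 kg | 3060 / 144 | 21.2 |
| Man 80, 70 kg | 4200 / 144 | 29.2 |
| Woman 60, 70 kg | 4760 / 144 | 33.1 |
| Man 70, 75 kg | 5250 / 144 | 36.5 |
| Man 55, 60 kg | 5100 / 144 | 35.4 |

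The first three fall below 30 and the last three do not.

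**Step 2: creatinine above which clearance falls below 30** = (140 − age) × kg × (0.85 if female) / (72 × 30 = 2160).

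- Woman 85, 50 kg: 2337.5 / 2160 = 1.08 mg/dL
- Woman 80, 60 kg: 3060 / 2160 = 1.42
- Woman 70, 60 kg: 3570 / 2160 = 1.65
- Man 85, 65 kg: 3575 / 2160 = 1.66
- Man 80, 70 kg: 4200 / 2160 = 1.94
- Under 60 by a non-renal route: woman 59, 50 kg, 3442.5 / 2160 = 1.59; man 59, 50 kg, 4050 / 2160 = 1.88

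All of these lie inside the permitted range.

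**Step 3: body weight below which creatinine 2.0 gives clearance under 30** = 4320 / [(140 − age) × (0.85 if female)].

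- Women: 62.7 kg at 59, 72.6 kg at 70, 84.7 kg at 80
- Men: 53.3 kg at 59, 61.7 kg at 70, 72.0 kg at 80

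**Step 4: size of the dose difference.** 1.8 / 1.2 = 1.5. At 60 kg, 60 × 1.8 = 108 mg against 60 × 1.2 = 72 mg per cycle.

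**Step 5: does anything else set the first dose by renal function?** Before registration, section 3.0 has the site call "for dose level and to ensure that a place on the protocol is open to the patient". That reads as assignment of the cohort's dose level and has no renal criterion. The weekly investigator call (7.1) has none either. Creatinine is measured before each cycle (4.0) and graded at each evaluation (10.54). The creatinine row in 8.2, however, applies at retreatment, acts on nivolumab and leaves BV unchanged. The accrual-suspension rule in 16.52 responds to Grade 4 or higher non-hematologic events. None sets a renal threshold before the first dose.

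**The case against.** The strongest reply is that 15.15 defers to the protocol, and the protocol specifies 1.8 mg/kg in three places. On that reading the condition is met and nothing is breached. Conversely, 15.15 is itself part of the protocol, so a site could treat it as the specific rule and start at 1.2 mg/kg, with no excess dose. Both readings are tenable. A reader might therefore infer that the plan contradicts itself, or that it definitely gives these patients 50% too much; the text supports neither. What stands is that the sections do not say which reading was intended.

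A reader might also infer that such patients will certainly be enrolled and harmed. The documents show only that entry is permitted. The profiles above are assumed, the weight limits in step 3 are taken at the highest permitted creatinine, and investigators may exclude some patients on judgement. The number could be zero. Section 15.15 reports exposure trends in both directions, without size or clinical outcome, so net harm from 1.8 mg/kg is not established. Rules in 8.2 reduce BV for Grade 2 neuropathy and Grade 3 low platelets, which limits later exposure though not the first dose.

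Finally, the primary objective in 2.11 includes patients with impaired renal function, so a floor may look contrary to the trial's purpose. It is not: 3.12 itself defines the renal route as 30 to below 60 mL/min, and that range stays eligible.

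**Conclusion.** The point holds as an unresolved starting dose in a group the eligibility criteria permit. Creatinine up to 2.0 mg/dL does not guarantee a clearance of 30 mL/min, and the patients who can fall below it are mainly older or lighter. If 1.8 mg/kg is applied to them, the dose is 50% above the recommendation; if 15.15 governs, there is no excess.

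This rests on the protocol's own equation and on assumed ages and weights. It assumes the safety phase does not move the whole trial to level -2, where BV is already 1.2 mg/kg. It covers only the renal half of the recommendation in 15.15; the hepatic half was not examined. It is worth correcting before enrolment, at medium confidence, because the number affected and the clinical effect are unknown.

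**What to change.** Add to 3.16, for all patients: *Cockcroft-Gault creatinine clearance of at least 30 mL/min*. This extends the floor already in 3.12 and uses age, weight and creatinine already collected at baseline. The cost is the loss of a few older or lighter patients from a trial aimed at an older, frailer group; the documents do not allow that number to be estimated. Sample size, decision rules and error rates do not change.

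Enrolling these patients at 1.2 mg/kg instead is a larger change, for four reasons:

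- Under 8.1 the next BV reduction is discontinuation, so no step is left.
- The platelet rule in 8.2, "then reinstitute BV at 1.2 mg/kg and resume nivolumab at same dose", would no longer reduce the BV dose. The Grade 2 neuropathy rule would likewise leave it unchanged.
- BV 1.2 mg/kg with nivolumab is not a level in 7.11, so 7.11, 16.4, 16.11 and 16.52 would have to say how these patients count.
- A lower dose could reduce ADC exposure further.

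If 1.8 mg/kg is intended for these patients, a sentence in 7.22 saying so, with the reason, would remove the ambiguity but leave the dose above the recommendation.
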